4.3 Subject Recruitment and Screening

Subjects will be recruited for this trial in several ways

1. A letter and attached flier will be sent to those enrolled in the University of Chicago Allergy and Asthma Research Registry
2. A short description will be posted in social media
3. Patients will be approached during clinic visits to the Allergy/Immunology clinic at the University of Chicago
4. Fliers will be sent to outside allergists

Subjects who respond to advertisement will first undergo a prescreen to confirm inclusion and exclusion criteria. Those who meet criteria will be invited in for a screening visit where skin testing, spirometry, blood draw, and questionnaire will be administered. Those who meet criteria after the screening visit will be randomized and enrolled.

4.4 Early Withdrawal of Subjects

4.4.1 When and How to Withdraw Subjects

Subjects may be withdrawn from this study at any time. Subjects may be withdrawn from the study prior to the completion of the study by the subject for safety reasons, failure of the subject to protocol requirements, subject consent withdrawal. Abrupt withdrawal from this study poses no additional risk to the subject.

4.4.2 Data Collection and Follow-up for Withdrawn Subjects

Even if subjects withdraw or are withdrawn prematurely from the study, data from the electronic medical record may continue to be used and patients may continue to be contacted, periodically by phone to determine if the patient has suffered any adverse events from withdrawal from the study if subjects allow contact to continue.

5 Study Food

5.1 Description

The following foods will be used:

- Fiber supplement: resistant potato starch
- Placebo: corn starch

5.2 Treatment Regimen

Subjects will be asked to take 1 tablespoon of fiber supplement (or placebo daily) mixed with a liquid or semi-solid food, such as pudding, applesauce or guacamole. If the supplementation causes abdominal distress, the participants will be asked to cut the dose in half for one week then increase back to the full tablespoon dose.

5.3 Method for Assigning Subjects to Treatment Groups

Subjects will be randomly assigned to either the treatment or placebo. Randomization will be conducted by IDS pharmacy. Study staff will be blinded throughout the course of the study. Subject compliance will

CONFIDENTIAL

This material is the property of the University of Chicago.
Do not disclose or use except as authorized in writing by the study PI

05.16.2023

be monitored by subject/parent self-report in paper diary provided to the subject at the start of the study as well weight of returned investigational product.

5.4 Prior and Concomitant Therapy

Subject will be asked to discontinue any daily antihistamine use. However, subjects will be allowed to use oral antihistamines on an as needed basis. A record of all current medications will be kept from the start to the completion of the study. A record of medications taken to manage POIT related side effects will be monitored in a daily diary. All study participants will be required to have an epinephrine autoinjector throughout the duration of the study. If the study participant is unable to obtain a new epinephrine autoinjector after the expiration, use or loss of a current epinephrine autoinjector, every effort will be made by the Principal Investigator to obtain one for the subject; however, if one cannot be obtained, the subject may be withdrawn from the study.

Please see exclusion criteria for medications not allowed during this study.

5.5 Packaging

The study food will be transferred from the original packaging into a sealed plastic container appropriately labeled.

5.6 Blinding of Study

Neither the study participant nor the study team will be aware of the contents of the sealed plastic container provided to the study participant²

Only the study pharmacist will have access to the form which links each study participant to their respective groups. The investigational product and placebo will be stored at the University of Chicago IDS pharmacy at:

[name]
[name]
[name]

5.7 Storage, Dispensing and Return

5.7.1 Storage

The study food may be stored at room temperature but should not be subject to extreme hot or cold. The study food should remain in the provided contained throughout the duration of the study. If the contents of the contained spill or become contaminated, the investigators will provide a new container of study food to the participant.

5.7.2 Return or Destruction of Study Device

At the completion of the study, any remaining study food will be returned to the investigator, and there will be a final reconciliation of the study food by weighing the container and its contents. All remaining study food will be destroyed by the IDS pharmacy.

6 Study Procedures

6.1 Visit 1

- Informed consent/assent
- Medical/allergy history
- Concomitant medications
- Vital signs
- Physical examination, including height and weight

CONFIDENTIAL

This material is the property of the University of Chicago.
Do not disclose or use except as authorized in writing by the study PI

05.16.2023

- Quality of life assessment
- Spirometry (if has asthma diagnosis; as COVID allows)
- eNO (if has asthma diagnosis; as COVID allows)
- ACT score (if has asthma diagnosis; as COVID allows)
- Skin prick testing
- Blood draw
- Stool sample kit given

6.2 Visits 2 and 3 (within 4 weeks of visit 1)

- Stool sample collection (visit 2 only)
- Vital signs
- Physical examination, including height and weight
- Spirometry (if has asthma diagnosis; as COVID allows)
- DBPCFC
- Randomization
- Prebiotic dispense

6.3 Visit 4 (30 days after visit 3)

- Interval medical history
- Vital signs
- Physical examination, including height and weight
- Spirometry (if has asthma diagnosis as COVID allows)
- Skin prick testing
- Blood draw
- Stool sample collection
- Collection of dose and symptom logs
- Standard of care consent for POIT
- POIT initial dose escalation day

6.4 Visits 5 (day after visit 4)

- Vital signs
- Physical examination, including height and weight
- POIT 3mg dose start

6.5 Visits 6-14 (every 2-4 weeks)

- Interval medical history
- Vital signs
- Physical examination, including height and weight
- Stool sampling (monthly)
- Collection of logs

6.6 Visit 15 (3 months after visit 14)

- Interval medical history
- Vital signs
- Physical examination, including height and weight
- Stool sample collection
- Collection of logs

Visit 15 (3 months after visit 14; virtual)

- Interval medical history

CONFIDENTIAL

This material is the property of the University of Chicago.
Do not disclose or use except as authorized in writing by the study PI

05.16.2023

- Height and weight
- Stool sample collection
- Collection of logs

6.7 Visits 16 and 17 (3 months after visit 15)

- Interval medical history (visit 16 only)
- Vital signs
- Physical examination, including height and weight
- Stool sample collection (visit 16 only)
- Skin prick test (visit 16 only)
- Blood draw (visit 16 only)
- Spirometry (if has asthma diagnosis; as COVID allows)
- DBPCFC

7 Statistical Plan

7.1 Sample Size Determination

As this study is an exploratory, pilot study we will enroll 30 subjects.

7.2 Statistical Methods

Chi-square testing (or non-parametric equivalent) will be used to compare categorical variables. Student's t-test (or non-parametric equivalent) will be used to compare continuous variables. Microbial relationships between samples will be compared using principal coordinate analysis and average-neighbor hierarchical clustering. Welch's t-test will be used to determine significant abundance differences between OTUs.

8 Safety and Adverse Events

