Exploratory Endpoints	
 To demonstrate the effect of resistant potato starch (RPS) on the fecal microbiome and metabolome To determine if gnotobiotic mice colonized with the fecal microbiota of study participants models clinical response To evaluate the immunological effects of fiber supplementation in children 
 Change in peanut specific IgE and IgG4 levels Change in peanut skin prick test mean wheal diameter Change in peanut component levels
Number of Subjects	30 peanut allergic subjects will be randomized 1:1 of dietary supplementation of a fiber supplement (RPS) versus placebo
Diagnosis and Main Inclusion Criteria	
 Age 4 to 17 (inclusive) A convincing clinical history of peanut allergy Immune markers consistent with peanut allergy 
 Serum IgE to peanut of >0.35 kUA/L and a skin prick test to peanut >8mm greater than the negative saline control –or– Serum IgE to peanut of >5 kUA/L and a mean peanut wheal diameter on skin prick test 3 to 8mm greater than the negative saline control –or– Serum IgE to peanut of >14 kUA/L and mean peanut wheal diameter on skin prick test 3mm greater than the negative saline control Experience dose-limiting symptoms at or before 100mg challenge dose of peanut protein on screening double blind placebo-controlled food challenge (DBPCFC) Written informed consent from parent/guardian Written assent from subjects above the ages 4-17

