In this study, we are enrolling subjects between the ages of 4 and 17, inclusive with peanut allergy and asking them to consume either a RPS or a control starch (corn starch). This consumption of either product may increase the overall caloric intake of subjects which may lead to weight gain. Subjects in the RPS group will be asked to consume 1 tablespoon (12 grams) of a fiber supplement daily which contains 40 calories/tablespoon. Subjects in the control group will be asked to consume 1 tablespoon (8 grams) of ACS daily which contains 30 calories/tablespoon. In addition, an increase in fiber consumption may lead to bloating, gas and/or constipation.

Risks Associated with DBPCFC

In this study DBPCFCs will be conducted in accordance with the recommended PRACTALL guidelines. The screening DBPCFC is utilized as the standard of care to confirm peanut allergy and does not confer higher than minimal risk than a open label food challenge used clinically to confirm peanut allergy prior to POIT. The screening DBPCFC will also establish a threshold for reactivity for comparison with the exit DBPCFC. The exit DBPCFC will be used to establish efficacy of POIT and confirm safety of accidental ingestion of peanut. The exit DBPCFC also does not confer more than minimal risk above a standard of care open label food challenge used during POIT to confirm tolerance of peanut ingestion. DBPCFC are expected to induce allergic reactions. Reactions range from mild (nausea, few hives) to severe (wheezing, diffuse urticaria, rhinitis/conjunctivitis, vomiting/diarrhea, impending doom) to potentially life threatening (low blood pressure, difficulty breathing, neurologic changes). Administered in a controlled setting under the supervision of experienced staff, food challenges are considered safe and are the

CONFIDENTIAL

current gold standard for the diagnosis of peanut allergy. As soon as symptoms consistent with an allergic reaction are witnessed, interventions to stop the reaction are begun (H1 antihistamines and epinephrine).

Risks Associated with POIT

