3.3 Secondary Study Endpoints

The secondary endpoints are as follows:

- To determine the proportion of subjects who experience dose related GI side effects during oral immunotherapy

CONFIDENTIAL

This material is the property of the University of Chicago.
Do not disclose or use except as authorized in writing by the study PI

05.16.2023

- To determine the proportion of subjects who experience hypersensitivity reactions (other than GI) during oral immunotherapy

The exploratory endpoints are as follows:

- To demonstrate the effect of resistant potato starch (RPS) on the fecal microbiome and metabolome
- To determine if gnotobiotic mice colonized with the fecal microbiota of study participants models clinical response
- To evaluate the immunological effects of fiber supplementation in children
 - Change in peanut specific IgE and IgG4 levels
 - Change in peanut skin prick test mean wheal diameter
 - Change in peanut component levels

4 Subject Selection and Withdrawal

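### Section 7.2 fixes no analysis scale, no baseline adjustment, no baseline visit and no single test for binary endpoints, although IgE, IgG4, component and wheal values are taken before randomisation

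*Combined protocol and SAP*

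**What the plan says.** Section 7.2 (repeated in the Study Summary) has one sentence for each type of variable: "Chi-square testing (or non-parametric equivalent) will be used to compare categorical variables" and, for Student's t-test, "or non-parametric equivalent) will be used to compare continuous variables". Apart from microbiome methods, that is the whole plan for comparing the arms. It names no transformation, covariate, baseline visit or rule for moving to the fallback test.

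Section 3.3 lists the serology and skin-test endpoints as exploratory and defines them as changes, for example "Change in peanut specific IgE and IgG4 levels". The schedule in section 3.1 and the visit lists in section 6 place skin test and blood draw at V1, V4 and V16, with arm randomisation at V3. The Study Summary describes skin testing as done at screening and exit. That hints at V1 for the wheal, but nothing in the plan defines a baseline for either measure.

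On the food challenge, section 1.5 states: "The screening DBPCFC will also establish a threshold for reactivity for comparison with the exit DBPCFC". No endpoint or analysis in sections 3.2, 3.3 or 7.2 makes that comparison. The primary endpoint (section 3.2) is binary. On size, section 7.1 states: "As this study is an exploratory, pilot study we will enroll 30 subjects".

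**The concern.** Three choices are left open that the analyst could settle after seeing the data.

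- **Scale and covariate.** IgE and IgG4 are usually right-skewed. A t-test on raw change is then dominated by the few children with high starting values. Section 7.2 permits that analysis, and equally permits a log-change t-test or a rank test.
- **Baseline visit.** V4 follows 30 days on randomised product. A change counted from V4 leaves out any effect of the lead-in, and a V4 covariate would adjust for something the treatment may have altered.
- **Binary test.** Chi-square is not a parametric test of means, so its non-parametric equivalent has no clear meaning. Fisher's exact test is the likely reading. At 15 per arm the two can disagree on the same table, and this affects the primary endpoint.

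At stake are precision in a very small trial and a result that should not depend on which permitted test was run.

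**Working it through.** **Inputs.** From the documents: 30 children (section 7.1) randomised 1:1 (Study Summary), so 15 per arm. The plan states no alpha, effect, SD, correlation or response rate, so there is no power figure to reproduce. Assumed here: two-sided 0.05; IgE halved by treatment (ln 2 = 0.693 on the log scale); log-SD 1.2 at both visits; baseline-to-exit correlation r of 0.5, 0.7 and 0.85.

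**Serology, by formula.** On the log scale, with common SD s:

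- variance of change = 2s²(1 − r)
- ANCOVA residual variance = s²(1 − r²)
- ratio, ANCOVA to change = (1 + r)/2, which is 0.75, 0.85 and 0.925 for the three correlations

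So ANCOVA on 15 per arm is worth 15/0.75 = 20, 15/0.85 = 17.6 or 15/0.925 = 16.2 per arm of a log-change t-test. At r = 0.7 the SD of log change is 1.2 × √0.6 = 0.93 and the ANCOVA residual SD is 1.2 × √0.51 = 0.86. The standardised effects are 0.693/0.93 = 0.75 and 0.693/0.86 = 0.81.

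**Serology, by simulation** (thousands of trials per row; repeat runs differ by a point or two):

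| r | t, raw change | Mann-Whitney, raw change | t, log change | ANCOVA, log |
|---|---|---|---|---|
| 0.5 | 13% | 21% | 33% | 40% |
| 0.7 | 18% | 31% | 50% | 55% |
| 0.85 | 29% | 51% | 80% | 81% |

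Raw to log change gains 20, 32 and 51 points. Log change to ANCOVA gains 7, 5 and 1 point (up to 8 at r = 0.5 in repeat runs).

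**A check without skewness.** For normal data with equal SDs and a true difference of 0.8 SD, 15 per arm, power for change t-test against ANCOVA is 43 and 58% at r = 0.3, 56 and 67% at 0.5, 78 and 83% at 0.7, and 92 and 93% at 0.8. The gain from adjustment shrinks as r rises.

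**Binary endpoints, exact enumeration of all 16 × 16 = 256 tables.** For 13/15 against 8/15, uncorrected chi-square = 30 × (13 × 7 − 2 × 8)² / (15 × 15 × 21 × 9) = 168,750/42,525 = 3.97, so p = 0.046. Fisher gives 0.109 and Boschloo 0.055. In 24 of the 256 tables chi-square is significant at 0.05 and Fisher is not.

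| Test | Maximum size | Power, 60% v 90% | Power, 50% v 90% |
|---|---|---|---|
| Fisher | 1.8% | 33% | 54% |
| Boschloo | 4.3% | 46% | 67% |
| Chi-square, uncorrected | 5.5% | 51% | 73% |

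The response rates are assumptions. The sizes and the example p-values depend only on 15 per arm.

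**Adjusting the binary primary endpoint for screening threshold.** In simulation with a five-level threshold and latent correlation 0.3 to 0.7, power moves by about −1 to +9 points (for example 60% v 90%: from 51% to 50, 53 and 59%).

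**The case against.** **Baseline is already used.** A reader might infer that section 7.2 throws away much of the trial's power by ignoring pre-randomisation values. The documents do not support that. The IgE, IgG4, component and wheal endpoints are changes, so the starting value enters. Nor does section 7.2 require the raw scale; a log-change t-test fits its wording and comes within about 1 to 8 points of ANCOVA. This objection stands, and it limits the point to what is left unspecified.

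**V4 is a natural baseline for immunotherapy.** It falls on the day oral immunotherapy starts. But the randomised comparison is starch against placebo, which starts at V3, so only V1 precedes treatment.

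**Boschloo is not the most powerful choice.** Correct. Uncorrected chi-square, which the plan names first, has about 5 points more power at 60% v 90%. Its maximum size of 5.5% is slightly above nominal. Boschloo is a gain in power only against Fisher; its case rests on size control. The necessary step is naming one test.

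**The exit ladder could be analysed as ordered doses.** A reader might infer from section 1.5 that an exit-threshold analysis adjusted for screening threshold is missing and would add much power. No such endpoint is listed, and eligibility restricts screening thresholds to 100 mg or below. A gain found with an ordinal outcome would come mainly from the finer outcome under an assumed model, not from the baseline. Section 8.4.3 also leaves some children unchallenged at exit. Placing them all in the lowest category could rank a child taking 150 mg daily with or below one who reacts to 1 mg.

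**It is a pilot, and serology is exploratory.** True, and no power is claimed. That lowers the severity, but the primary endpoint is subject to the same open choice of test.

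**Conclusion.** The point holds as a gap in prespecification: no scale, no baseline adjustment, no baseline visit and no single binary test. Its best-supported part is the binary test, because the conflict between chi-square and Fisher needs no assumption beyond 15 per arm and reaches the primary endpoint.

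For serology the possible loss is large only if raw change is analysed. It is then about 27 to 52 points against log ANCOVA over the assumed correlations (40 − 13 at r = 0.5; 81 − 29 at r = 0.85), nearly all of it due to scale. These sizes rest on an assumed effect, log-SD and correlation and should be read as a range. A substantial gain from adjusting the primary endpoint for screening threshold is not shown. The change should be made, but it is a matter of wording and does not invalidate the design.

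**What to change.** Amend section 7.2, and the matching Study Summary text, before unblinding:

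- **Serology and wheal.** Compare arms by ANCOVA of the V16 value with the V1 value as covariate. Use the log scale for IgE, IgG4 and components, and the original scale for wheal. State that V1 is the baseline and that V4 is a post-randomisation measurement.
- **Binary endpoints, including the primary.** Replace the chi-square-or-equivalent wording with one named test, such as Boschloo's exact test, reported with a 95% confidence interval for the risk difference.
- **Optional.** A supportive ordinal analysis of the exit challenge may be added, but only with a considered rule for children who are not challenged. It should not be justified by a power claim.

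The cost is a change of wording and standard software, with no new visits or samples. Serology results would be reported as ratios, and the plan would need a rule for values below the assay limit before logs are taken. Boschloo gives up about 5 points of power against uncorrected chi-square at 60% v 90%, in return for a maximum size below 5% and no choice of test after the data are seen.

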2.2 Secondary Objective(s)

The secondary objectives of this study are:

- To determine if prebiotic therapy influences the gut microbiome/metabolome
- To determine if prebiotic therapy influences immunological markers associated with peanut allergy

3 Study Design

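### Section 7.2 names no community-level test of arm: ordination and clustering of stool samples describe the microbiome but cannot determine whether RPS changed it

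*Combined protocol and SAP*

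**What the plan says.** Section 7.2, repeated in the Statistical Methodology row of the Study Summary, gives the microbiome two sentences. For the community as a whole: "Microbial relationships between samples will be compared using principal coordinate analysis and average-neighbor hierarchical clustering". For single taxa: "Welch's t-test will be used to determine significant abundance differences between OTUs". The general rule for other data is "Student's t-test (or non-parametric equivalent) will be used to compare continuous variables", but no community summary (axis score, diversity index, distance from baseline) is named as a variable to which it applies. The documents give no distance measure, no time point and no rule for repeated stools from one child.

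The question to be answered is stated twice. Section 2.2 makes it a secondary objective: "To determine if prebiotic therapy influences the gut microbiome/metabolome". Section 3.3 places it among the exploratory endpoints: "To demonstrate the effect of resistant potato starch (RPS) on the fecal microbiome and metabolome".

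On size, Section 7.1 reads in full: "As this study is an exploratory, pilot study we will enroll 30 subjects". The Study Summary sets 1:1 allocation, so 15 per arm.

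Stools are collected at visit 2 (Section 6.2), visit 4 (6.3), monthly over visits 6 to 14 (6.5), visit 15 (6.6) and visit 16 (6.7). The Schedule of Procedures puts arm randomisation and dispensing at visit 3, so the visit 2 stool is a true baseline.

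**The concern.** The objective is inferential, while the community-level methods are displays. Principal coordinate analysis always returns coordinates, and hierarchical clustering always returns clusters, whether or not RPS does anything. Neither takes arm as input, and neither states how often the picture would look as it does by chance.

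Whoever writes the results must then either describe the plots by eye or choose a test, a distance, a time point and a unit after seeing the data. The choice of unit is the most hazardous. The sentence in 7.2 speaks of samples, and stools from one child resemble each other, so a sample-level comparison can mistake differences between children for a difference between arms.

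**Working it through.** **1. No figure to reproduce.** The plan gives no alpha, power, effect size or SD. For scale only, assuming two-sided 0.05 and 80% power, one continuous measure with 15 per arm can detect (1.96 + 0.84) × √(2/15) = 1.02 SD. With 12 per arm (an assumed 20% loss) it is 2.80 × √(2/12) = 1.14 SD. Any test here can find only large effects.

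**2. Stools per child.** Visits 2, 4, 15 and 16 give 4. The Schedule of Procedures runs visits 6 to 14 from day 16 to month 8, so monthly collection adds about 7. The total is about 11, of which about 10 are on supplement. With 30 children that is 30 × 11 = 330 samples.

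**3. Cost of ignoring the child, for a single measure.** With m stools per child and within-child correlation ρ, the variance of an arm mean is understated by 1 + (m − 1)ρ.
- Assume m = 10, ρ = 0.6: 1 + 9 × 0.6 = 6.4, and √6.4 = 2.53. A nominal 1.96 is really 1.96/2.53 = 0.775, so the two-sided false-positive rate is about 44%.
- Assume between-child SD 1.0, within-child SD 0.7, m = 11: ρ = 1/(1 + 0.49) = 0.67, the factor is 1 + 10 × 0.67 = 7.7, and 1.96/2.78 = 0.706. The rate is about 48%.

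**4. The same at community level, by simulation.** Assumptions: 150 taxa, log-normal abundances, Bray-Curtis distance, 15 children per arm, 11 stools each, between-child SD 1.0 and within-child SD 0.7 on the log scale. The test is a permutation test on the between-arm sum of squares of the distances, with p = (1 + number of permuted values at least as large as the observed)/(1 + number of permutations).

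| No RPS effect | Rejected at 0.05 |
|---|---|
| Two-cluster cut of average linkage | no test; two clusters in 100% of 400 runs |
| All 330 samples treated as independent | 100% of 150 runs |
| Permuted between children, one stool each | 4.3% of 400 runs |
| Permuted between children, child mean | 4.0% of 400 runs |

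The Monte Carlo standard error at 5% is √(0.05 × 0.95/400) = 1.1 points, so the last two rows agree with the nominal level. The first two principal coordinates carried on average 27% of the positive eigenvalue total with no effect present: axes with apparent structure appear regardless.

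**5. What the child-level test can find.** Under the same model, a shift of 1.0 log unit in 15 of 150 taxa was detected in 71% (one stool) and 91% (child mean) of runs, and a shift of 0.5 in 8% and 7%. The mean abundance profile was redrawn between settings, so these are not points on one power curve.

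**6. Illustration only: a cluster-by-arm table, which the plan does not state.** Assumptions: 60 taxa, log SD 1.2, within-child correlation 0.6, 10 stools. With no effect, a sample-level chi-square of four clusters by arm gave p < 0.05 in 73% to 78% of trials, and 98% if all taxa had equal mean abundance. With 6 taxa raised by 1.5 log units (e^1.5 = 4.5-fold), a child-level two-cluster Fisher test found the shift in 9% to 13%, against 88% to 100% for the child-level permutation test. With one stool per child it was 3% to 4% against 68% to 85%. The ranges span separate runs, including different spreads of mean abundance across taxa.

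**The case against.** The strongest reply is that this is a 30-child pilot with the microbiome effect listed as an exploratory endpoint, that ordination and clustering are ordinary exploratory displays, and that 7.2 does contain a microbiome test. Section 1.1 singles out particular taxa, above all *R. bromii*, as the expected responders, and a per-OTU Welch test addresses that directly. On the scenario in step 6 of the working, Welch tests on log abundance with the child as unit and Bonferroni over 60 taxa flagged at least one OTU in 76% to 99% of trials. Student's t-tests on the first two coordinates, Bonferroni-corrected, found the shift in 64% to 100%.

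Much of this stands, and it rules out three stronger readings that a reader might infer.
- That a real shift would usually be missed. The documents do not support this: that result belongs to a two-cluster split by arm, and the plan's other tests could well detect such a shift.
- That the plan's error rate is 73% or more. Section 7.2 never says that clusters will be tabulated against arm.
- That the whole secondary objective rests on visual grouping. The objective concerns the microbiome and metabolome broadly, and the OTU tests can serve part of it.

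What does not stand is that these tests fill the gap. The Welch sentence does not name arm as the contrast, and the plan states neither log scale, nor child as unit, nor multiplicity control. On raw relative abundance with Bonferroni, the detection rate fell to 39% to 40%. Without correction, at an assumed 0.05, 100 null OTUs give 100 × 0.05 = 5 expected false positives, and at least one with probability 1 − 0.95^100 = 99.4% if independent. No t-test on coordinates is specified either. Pilot status excuses low power; it does not supply a test for a stated objective.

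**Conclusion.** The point holds at community level and no further. As written, the plan offers no inference on whether overall composition differs between RPS and placebo. This follows from the text of 7.2 and needs no assumption. The warning about repeated stools also holds: under plausible within-child correlation, a sample-level comparison has a false-positive rate of roughly 44% to 48% for one measure, and reached 100% in the community simulation. Those sizes, and all the power figures, depend on assumed variances, taxa counts and shifts, because the documents give none. The near-nominal level of the child-level test depends on much less, since permuting arm between children mirrors the randomisation.

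The weight is moderate: this should be changed, but the endpoint is exploratory and the primary endpoint is not touched. Even after the change, a non-significant result from 15 per arm would not show that RPS has no effect.

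**What to change.** Keep the ordination and clustering in 7.2 as descriptive figures. Add two sentences, labelled exploratory, that state:
- a permutation test of arm, for example PERMANOVA, on one distance named in advance, such as Bray-Curtis;
- the data used: either one named on-supplement time point (visit 4, after 30 days of supplement, is one candidate) or one on-supplement summary per child;
- arm labels permuted between children, never between samples, and within blocks or strata if the pharmacy's randomisation uses them;
- the visit 2 stool taken into account, for example through its leading coordinates as covariates;
- a check of dispersion by arm, so that a difference in spread is not read as a shift.

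Other child-level tests of arm would also serve; what matters is that one is named before unblinding. The cost is two sentences and a little more analysis on samples already planned, with no added visits or stools.
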